5.2 EXCLUSION CRITERIA

An individual who meets the following criteria will be excluded from participation in this study:

1. Is a professional, paid caregiver (e.g., home health aide)

2. Anything that would preclude safe or meaningful participation in the study

5.3 LIFESTYLE CONSIDERATIONS

During this study, participants are asked to:

- Wear a Fitbit® 24 hours/day, except when charging during the 10-day run-in period and 6-month (180 day) home monitoring period.
- Install the CareQOL app and Fitbit® app on their personal mobile device, and keep these apps installed for the duration of the study (~375 days).

5.4 SCREEN FAILURES

Screen failures are defined as participants who consent to participate in this study but are not subsequently assigned to the study intervention or entered in the study. Screen failures are unlikely in this study because eligibility assessment occurs pre-informed consent. However, if during the 10-day run-in period before the 6-month home monitoring period starts the study team is made aware of something that would change their eligibility, the participant will be noted as a screen failure.

5.5 STRATEGIES FOR RECRUITMENT AND RETENTION

Recruitment: Two sites (University of Michigan [U-M] – Ann Arbor, MI; and Baylor College of Medicine [BCM] - Houston, TX) will be used to recruit participants (care partners of persons with TBI) for this study. Sites will recruit participants primarily through their established medical and TBI clinics, participant registries (both TBI- and care partner-specific registries), and clinical databases. Study participants will also be recruited through local TBI and care partner support groups, from organizations like the Brain Injury Association, and through targeted Facebook ads.

Recruitment and retention methods used in this study will be approved by the Institutional Review Board at U-M (U-M IRBMED; serving as the single IRB for this study for BCM and U-M) and are detailed in the IRBMED submission. Potential participants will be recruited directly or through the person they are caring for. Individuals who are interested in participating will be encouraged to ask questions about the study and their participation, and if they opt to enroll, they will provide informed consent prior to completing any study assessments.

In order to ensure that recruitment targets are being met, teleconference calls with the study recruitment teams by the project manager will be conducted to review progress, discuss problems, and guide additional recruitment efforts to meet stratification goals. Stratification goals (e.g., race, ethnicity, gender, etc.) can be found in the manual of procedures for this study.

Retention: Given the intensive nature of this study, we expect that participants will miss some daily assessments and have times when they do not wear the Fitbit®; our retention plan is focused on minimizing these missed assessments and engaging participants throughout the study.

Retention will be facilitated by several strategies:

- App development will consider factors known to increase participant engagement including strategies to target engagement and minimize fatigue (easy to navigate platform, app tailoring based on Fitbit® sensor feedback, etc.).³⁰ The app will also include a study team dashboard that we will use to monitor participant engagement.
- User guides and contact information for the study team (phone and email) will be supplied to participants and they will be encouraged to contact the study team with any questions or concerns.
- When enrolling participants, we will offer participants a choice of wristbands; they can select the wristband that is most comfortable and visually appealing to them. If they are not happy with their selection, we will provide an alternate wristband.
- Study staff will maintain regular contact with the study participants. All study participants will be contacted at least once during the study run-in period, at least once during the first week of the 6-month home monitoring period and at least once each month during the remaining months of the 6-month home monitoring period.
- Participants who do not complete any study assessments (e.g., uploading Fitbit® data or answering EMAs) for several days will receive a reminder from the study team.
- In case of lost equipment/equipment failure during the run-in and home monitoring periods, we will send replacements as supplies allow.

Participant Incentives: We will compensate participants for their time and inconvenience, as follows:

- Baseline assessment, final 6-month home monitoring assessment, 3-month post-monitoring assessment, 6-month post-home monitoring assessment: Participants will receive \$20 for completing each survey (\$80 total possible).
- Monthly HRQOL surveys during the home monitoring period: Participants will complete end of month surveys during the home monitoring period. Participants will receive \$10 for completing each end of month survey for months 1-5 (\$50 total possible).
- Daily EMA assessments and Fitbit® data during the 6-month home monitoring period: Participants will receive \$1 per day for each day that they have EMA and/or Fitbit® data during the six-month (180 day) home monitoring period (\$180 total possible).
- Participants who complete the study will be allowed to keep the Fitbit® that they use in the study.
- Compensation will occur monthly to encourage prompt responding.
- We may send out nominal value items (e.g., notepads, pens) throughout the duration of study participation to encourage engagement.

6 STUDY INTERVENTION(S) OR EXPERIMENTAL MANIPULATION(S)

6.1 STUDY INTERVENTION(S) OR EXPERIMENTAL MANIPULATION(S) ADMINISTRATION

All participants will receive a Fitbit® for the collection of sleep and activity (steps) data, and will download the Fitbit® app and study app, CareQOL, on their personal mobile device (iOS or Android). The CareQOL app will deliver ecological momentary assessments (EMAs) once per day, compile and display data (including that collected on the Fitbit®), and deliver study notifications, including messages for the

participant to complete the daily EMA and other study surveys as well as delivering the personalized study intervention prompts to the intervention group (Just-in-time adaptive intervention [JITAI] group).

All study participants will complete 3 EMA questions daily on the CareQOL app. Each participant will be prompted by a push notification in a five-hour window (based on participant preference) from the app to answer the questions. The EMA questions are comprised of: 1 question on caregiver strain (taken from the TBI-CareQOL Caregiver Strain item bank), 1 question on anxiety (taken from the PROMIS Anxiety item bank) and 1 question on depression (taken from the PROMIS Depression item bank). Questions are on a five-point scale, with higher scores indicating more of the named construct.

In addition to the collection of the EMA data, the app compiles and displays a graphical summary of historical data for caregiver stress (strain), worry (anxiety), sadness (depression), steps (collected by the Fitbit®) and hours of sleep (collected by the Fitbit®) on a participant dashboard. Participants can view this information for the past week, past month or past year. This is available to all participants as a pull – that is, it is available at all times but is accessed only if the user chooses to access it.

In this study, half of the participants will be randomized to receive the intervention (JITAI; described below); the remaining participants will be in the control group, who will not receive the JITAI but will complete the activities already described in this section. Participants who are randomized to receive the JITAI will have a 50/50 chance of receiving the intervention each day.

The JITAI aims to promote behavioral change through motivational messages that are delivered through the CareQOL app as push notifications. These notifications provide a trigger for participants to initiate or continue behavior change and/or monitor behaviors (through engagement with the with the app). The push notifications are low burden: participants can personalize the administration time (in a 5-hour window) and notifications can be viewed quickly on their phone's lock screen. Participants can also choose not to engage with the notification at the time it is sent if it is inconvenient – they can return to it later if needed.

The JITAI push notifications are aimed at promoting healthy behaviors (physical activity and good sleep hygiene) and improving mood (anxiety, depression, caregiver strain). If receiving a notification, the message will be randomly drawn from this pool of messages. Some messages will use participants' data directly in the messages (e.g., You walked an average of 8,120 steps this week), and most of messages will be personalized based on data (e.g., someone with low steps will get a different message than someone with medium steps than someone with high steps; high-medium-low). Messages are comprised of one or more of the following different types: 1) Data feedback; 2) Facts; 3) Tips; and 4) Support. Randomization of the days the participants receive messages and the message the participant receives from the pool will be done through the CareQOL app.

The study intervention period is 180 days (6 months); in addition, there is an ~10-day run-in period where participants will install/adjust/troubleshoot the study technology and the app will gather baseline data to use to tailor messages once the intervention period begins.

6.2 FIDELITY

For this study, the intervention will be administered via the CareQOL app. The study team will conduct training during the baseline visit with each participant which will include:

- Helping the participant download and register for the CareQOL and Fitbit® apps on their personal device
- Helping the participant set any relevant app settings (e.g., make sure alerts are turned on/off, privacy settings, etc.)
- Demonstrating the CareQOL app features to the participant (e.g., participant dashboard, etc.)
- Ensuring that the participant understands the importance of entering the daily ratings and wearing the Fitbit®
- Explaining the relationship between the daily ratings and Fitbit® data and the intervention prompts (JITAI group only)
- Demonstrating how to sync the Fitbit® (including using the Fitbit® app) and how to enter the daily ratings in the CareQOL app

During the 10-day run-in period between the baseline visit and the start of the intervention, study team members will assist participants to make sure that participants can:

- Successfully wear and sync the Fitbit®
- Successfully respond to the EMA prompts

Participants who are unable to successfully complete the run-in period will be terminated from the study and noted as a screen failure.

Training and training materials will be provided to all study team members. New study members will undergo training before the study is started. Training will be documented in the electronic regulatory binder.

Participant adherence to the protocol will be assessed throughout the study. Study staff will have access to the CareQOL app dashboard which can be used to monitor participant engagement and adherence with the app. Specifically, study staff will monitor:

- Adherence to EMA entry
- Adherence to Fitbit® use/syncing
- Adherence to completing the end of month surveys (~30, 60, 90, 120, 150, 180 day)
- Adherence to completing the 3-month (~270 days) and 6-month (~360 days) post-intervention surveys

Adherence will be calculated as a percentage for each of these areas for all participants who are not withdrawn or lost to follow-up.

6.3 CONCOMITANT THERAPY

There are no concomitant treatment or management strategy restrictions for this study. Information about current treatments (medications and non-medications) will be collected at baseline. Changes in treatments will be captured at the end of month 3 (~90 days) and month 6 (~180 days) during the home monitoring period, and 3-months (~270 days) and 6-months (~360 days) post-home monitoring period.

7 STUDY INTERVENTION/EXPERIMENTAL MANIPULATION DISCONTINUATION AND PARTICIPANT DISCONTINUATION/WITHDRAWAL

7.1 PARTICIPANT DISCONTINUATION/WITHDRAWAL FROM THE STUDY

Participants are free to withdraw from participation in the study at any time upon request.

An investigator may discontinue a participant from the study for the following reasons:

- Lost-to-follow up; unable to contact participant (see **Section 7.2, Lost to Follow-Up**)
- Any event or medical condition/situation that occurs that would indicate that continued collection of follow-up study data would not be in the best interest of the participant or might require treatment that would confound the interpretation of the study
- The participant meets an exclusion criterion (either newly developed or not previously recognized) that precludes further study participation
- The participant is non-compliant with the study protocol

The reason for participant discontinuation or withdrawal from the study will be recorded. Participants who sign the informed consent form and are randomized but do not complete the 10-day run-in period will be replaced. Participants who withdraw or are discontinued before the end of the 6-month (~180 day) home monitoring period will be replaced.

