4 STUDY DESIGN

4.1 OVERALL DESIGN

Study Design: This behavioral trial will use a two-arm randomized controlled design. Each of the up to 280 care partner participants will be randomized to an active “JITAI” arm or to a control arm. The random allocation of participants to the treatment arm or control arm establishes the basis for testing the statistical significance or difference between the groups in HRQOL (caregiver strain, depression and anxiety).

Randomization: Blocked randomization will be used to limit bias and achieve an equal distribution of participants to the control and treatment arms. A randomization list will be generated for each site and the study statistician will oversee randomization. The participant will be randomized once he/she is deemed eligible and has provided informed consent (i.e. at Enrollment prior to baseline data collection). The study coordinator/research assistant who consented the participant will use their site’s randomization list to assign the participant to the correct study arm.

Duration of Study Participation: Study participation for both arms of the study (control and JITAI) involves a baseline assessment, followed by an approximate 10-day run-in period then a 6-month (180 day) home monitoring period (in which the intervention will be administered to the JITAI group). After the completion of the 6-month (180 day) home monitoring period, post-intervention surveys will be administered at 3 months (90 days) and 6 months (180 days) after the end of the 6-month (180 day) home monitoring period. Thus, the total duration of the study is ~375 days.

Study Sites: This is a multi-site study involving two sites: University of Michigan and Baylor College of Medicine. University of Michigan is the lead site and their IRBMED will serve as the single IRB for this study.

Study Intervention: The just in time adaptive intervention (JITAI) uses sensor data derived from the Fitbit® (e.g., accelerometer-based estimates of physical activity and sleep) and real-time self-report ratings (assessed once daily) of HRQOL (caregiver strain, depression, anxiety) to deliver personalized “pushes” to participants via a study specific app (CareQOL app). The personalized pushes will be delivered on ~50% of the days over the 6-month intervention period.

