9.3 POPULATIONS FOR ANALYSES

The primary and secondary endpoints will compare the JITAI group with the control group. Tertiary analyses may also compare important subgroups (e.g., caregiver groups that differ by relationship type [parent vs. spousal caregivers], caregiver groups that differ by sex [male vs. female caregivers], caregiver groups that differ according to the functional status of the person with TBI (e.g., complicated mild vs. moderate vs. severe TBI or perceived functional status based on Mayo Portland Adaptability Index scores).

The analyses will be an intention-to-treat approach where the participant will contribute data to the arm he/she was randomized to regardless of the amount of data contributed (i.e. the duration of participation).

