This protocol uses the University of Michigan definition of a protocol deviation (<https://az.research.umich.edu/medschool/glossary/deviation>) which defines a protocol deviation as “an incident involving non-compliance with the protocol, but one that does not have a significant effect on the subject’s rights, safety or welfare, and/or on the integrity of the data. Deviations may result from the action of the participant, researcher or staff.”

We will follow the U-M IRBMED reporting guidance for protocol deviations found here <https://az.research.umich.edu/medschool/guidance/other-reportable-information-or-occurrence-orio>.

Reportable protocol deviations will be reported and tracked in the REDCap database and will be discussed at investigator and project staff meetings.

The following events will not be reported as protocol deviations:

- A protocol deviation will not be reported for participants who skip/do not complete study survey questions or entire surveys (like end of month assessments or post-intervention surveys). Participants can decline to answer any survey question for any reason. We expect in an intensive, long duration protocol like this that participants may miss some assessments.
- A protocol deviation will not be reported for out-of-window assessments. Use of this data will be assessed by the study investigators for each study analysis; some analyses may need tighter compliance to the assessment window while others will not.
- A protocol deviation will not be reported for participants who miss/do not complete the EMA assessments or do not wear/miss uploading Fitbit® data during the home-monitoring period. For example, we expect that there may be instances where participants are unable to complete the

EMA assessments (for example, they are somewhere where it is inconvenient for them to answer) or forget to put on or sync the Fitbit®.

- A protocol deviation will not be reported for participants who decline the participant payment. It has been our experience that some research participants do not wish to receive payment for their participation in research studies.

Reportable protocol deviations will be reviewed at the project staff and investigator meetings, and summarized in the ISM report that it submitted to the U-M IRBMED and NINR at annual review (coinciding with the scheduled continuing review) and in other ISM reports (if applicable).

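### Section 7.1 lets an investigator discontinue a randomized participant from the whole study for undefined non-compliance and replace them, with no provision to collect the day-180 survey afterwards

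*Combined protocol and SAP*

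**What the plan says.** Section 7.1 introduces its list with "An investigator may discontinue a participant from the study for the following reasons", so the exit is from the study and not only from the intervention. One listed reason is "The participant is non-compliant with the study protocol", with no definition or threshold. The section then states: "Participants who withdraw or are discontinued before the end of the 6-month (~180 day) home monitoring period will be replaced".

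These exits come after randomization, which section 4.1 places "at Enrollment prior to baseline data collection". The same holds for run-in failures. Section 6.2 says "Participants who are unable to successfully complete the run-in period will be terminated from the study and noted as a screen failure", and section 7.1 says that those who are "randomized but do not complete the 10-day run-in period will be replaced".

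Three other parts of the protocol bear on the point:

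- Section 9.3 commits to intention-to-treat: "the participant will contribute data to the arm he/she was randomized to regardless of the amount of data contributed".
- Section 10.1.3 keeps the data of participants who withdraw.
- Section 10.1.8 treats missed ratings as expected: "A protocol deviation will not be reported for participants who miss/do not complete the EMA assessments". It says the same of skipped surveys and unworn or unsynced devices.

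The primary endpoint (section 3) is change in Caregiver Strain from baseline to day 180. Section 9.4.1 names a two-group t-test for inference, and 9.4.2 adds a random-intercept mixed model. Section 9 gives no missing-data method, no sensitivity analysis, and no rule for how a replaced participant and the replacement enter the analysis.

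**The concern.** A participant who stops using the app or the Fitbit can usually still answer a short survey at day 180. Section 7.1 allows that person to be dropped from the study before the survey is requested. Staying in the intention-to-treat set does not supply a day-180 score that was never collected.

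The decision is made after randomization, on an undefined criterion. It is informed by adherence that staff can watch on a dashboard (section 6.2), in a trial where site staff assign the arm from the list (section 4.1). If removal differs between arms, or relates to outcome differently in each, the observed comparison is no longer the randomized one. Enrolling replacements brings the count back up but does not recover the missing outcomes. Replacement is a live part of the plan: the amendment history gives it as one of two reasons for raising enrolment from 240 to 280.

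**Working it through.** **1. The plan's own figure.** Section 9.2 uses a difference of 4.0, SD 9.66, 80% power and two-sided 0.05. n per group = 2 x (1.960 + 0.842)^2 x 9.66^2 / 4.0^2 = 91.6, so 92. This matches the stated 92 (the noncentral t gives 93).

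**2. Loss of numbers is not the main problem.** Power = Phi(4.0/SE - 1.96), with SE = 9.66 x sqrt(2/n). The plan states 15% attrition, for its exploratory table only.

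- 120 per arm x 0.85 = 102: power 84.1%.
- 140 per arm x 0.85 = 119: power 89.1%.

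Both exceed 80%, so the issue is who is missing, not how many.

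**3. What each analysis can use after a discontinuation.**

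- *t-test on day-180 change:* needs the day-180 score, so the participant drops out of the test.
- *Mixed model (9.4.2):* can use monthly scores from days 30-150 collected before the exit. This protects the estimate to the extent that the missingness is explained by the observed data.
- *Run-in failure:* exits before the first monthly survey, so has no post-baseline monthly score for either analysis.

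**4. Size of bias in an observed-case comparison.** Let p be the share removed in an arm, and D the mean day-180 change in those removed minus that in those retained (higher strain is worse). The all-randomized mean is the retained mean + p x D. The error in the observed arm difference therefore has size p_JITAI x D_JITAI - p_control x D_control, or (p_JITAI - p_control) x D when D is the same in both arms.

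The documents give neither p nor D. Assumed: p_JITAI 5-15%, p_control 0-5%, D 3-6 T points.

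| JITAI removed | Control removed | D = 3 | D = 6 |
|---|---|---|---|
| 5% | 5% | 0 | 0 |
| 5% | 0% | 0.15 | 0.30 |
| 15% | 5% | 0.30 | 0.60 |
| 15% | 0% | 0.45 | 0.90 |

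The range is 0 to 0.9 points; 0.9 / 4.0 = 22.5%, about 23% of the target difference. With these signs the error favours JITAI. If more control participants are removed, or those removed did better than those retained, the sign reverses.

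**5. Effect on the test,** taking 120 observed per arm (SE = 9.66 x sqrt(2/120) = 1.247):

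| Bias | Rejection rate with no true effect | Power at a true 4.0 if bias is toward the null |
|---|---|---|
| 0 | 5.0% | 89.4% |
| 0.3 | 5.7% | 84.3% |
| 0.6 | 7.7% | 77.8% |
| 0.9 | 11.1% | 70.0% |

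**The case against.** The strongest reply is that the plan already has most of the safeguards. Section 9.3 foresees shortened participation and keeps each person in the randomized arm, 10.1.3 retains earlier data, and the mixed model can use monthly scores. Section 7.1 records the reason for each exit, and 7.2 requires repeated contact attempts when the day-180 survey is missed. Discontinuation is a discretionary power, and missed ratings are met with reminders (5.5). Enrolment already has a ceiling of 280, and everyone is assigned from a site list. All of this stands, and it is why intention-to-treat is weakened and not abandoned. None of it says that a discontinued participant is asked for the day-180 survey. Section 7.2 covers people who miss that survey, not people already taken off study.

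A reader might infer more than the documents support:

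- *That those removed are the ones for whom the app is not working, so that the bias favours JITAI.* The adherence monitored under 6.2 is daily ratings, Fitbit use and surveys, which are the same tasks in both arms. Response to the JITAI messages is not on that list. Differential removal is possible but not shown.
- *That 7.1 flatly contradicts 9.3 and 10.1.8.* Section 9.3 is compatible with early exit, and 10.1.8 defines what is reported as a deviation, not what counts as non-compliance. The fair statement is that 7.1 leaves open whether conduct tolerated in 10.1.8 can lead to removal.
- *That the deciding investigator knows the arm.* Section 4.1 has the coordinator or research assistant assign it; the documents do not say what the investigator knows.

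**Conclusion.** The concern holds as a rule in 7.1 that can cause avoidable loss of primary-endpoint data after randomization. It does not show that biased loss will occur. That day-180 collection stops is inferred from the wording of study discontinuation together with the absence of any rule for continued collection.

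Under the assumed shares and outcome differences, the bias in the day-180 t-test runs from 0 to 0.9 T points (0-23% of the 4-point target), with direction unknown. The zero end is real: equal removal with the same outcome difference in both arms gives no bias. At the upper end the false-positive rate would be about 11%, or, if the bias ran toward the null, power about 70%. The mixed model would reduce the bias where earlier monthly scores explain the missingness. The change is worth making because the loss is avoidable and the remedy is small.

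**What to change.** In section 7.1:

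- Separate stopping the app, Fitbit or daily ratings from stopping outcome surveys, and remove non-compliance as a reason to stop outcome surveys. What conduct justifies ending the other study activities is for the sponsor to define and to reconcile with 10.1.8.
- State that the day-180, 270 and 360 surveys are sought, by app or interview, from all randomized participants unless consent is withdrawn or the existing best-interest ground applies.
- State that replacements take the next entry on the site list, within the existing ceiling of 280.

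In section 9.3, state that discontinued and replaced participants stay in the analysis in their randomized arm, including those randomized who then fail the run-in.

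The means already exist: monthly and follow-up surveys may be done by interview (8.1), the app has an assessment-only mode (8.1.4.2), and these three surveys are paid at $20 each (5.5). The cost is protocol wording, a few more reminders and those payments.
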